4. TTLB
5. Rate of pregnancy loss for the first (and successive) IVF/ICSI stimulation cycle(s)
6. Rate of multiple pregnancy for the first (and successive) IVF/ICSI stimulation cycle(s)
7. Number of cancelled cycles for the first (and successive) IVF/ICSI stimulation cycle(s)
8. Number of OHSS cases for the first (and successive) IVF/ICSI stimulation cycle(s)

An additional secondary objective describes treatment-associated costs. Hence, the secondary objective 9 is to describe the following outcomes for the rhFSH-alfa reference product, HP-hMG and rhFSH-alfa biosimilar products individually and overall, across all products:

9. Costs associated with IVF/ICSI treatment (including drugs and other treatments), miscarriage/birth, and adverse events (i.e., OHSS)

9 Research Method

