9.2.2 Definition of Study Cohorts and Description of Treatments

Among the women included in the study, three study cohorts will be created at the level of the IVF/ICSI stimulation cycle based on which drug the woman received for COS: rhFSH-alfa reference product, HP-hMG or rhFSH-alfa biosimilar product. Only one type of gonadotropin use will be allowed for each stimulation cycle. Hence, cycles where mixed gonadotropin use was observed will not be included in the study. Mixed gonadotropin use may occur for example if, at prescription refill at the pharmacy, the drug (brand) on the written prescription was exchanged for an equivalent drug (same active substance, strength, formulation; therapeutically equipotent).

A woman may contribute maximum five stimulation cycles to the same cohort if she had several cycles with the same study drug. She may contribute cycles to more than one study cohort if she had distinct stimulation cycles with different study drugs. Between stimulation cycles with a study drug, a woman may have received a non-study gonadotropin for COS. History of IVF/ICSI treatment, including with a non-study gonadotropin, will be controlled for in the analysis (in the PS estimation). Overall, no more than five stimulation cycles and only up to the fifth stimulation cycle will be considered in this study, regardless if all cycles were observed in the study period and the type of gonadotropin used for COS.

FET cycles originated from an IVF/ICSI stimulation cycle included in the study will be assigned to the same cohort as that stimulation cycle. FET cycles originated from a stimulation cycle in which one of the study drugs was used but which was not included in the study (e.g., because of PGT), will not be considered. Different methods for cycle linkage will be used for Denmark and Sweden. For Sweden, the IVF register includes information enabling an FET cycle to be linked to the stimulation cycle it originated from. This information is the follicular aspiration date, which is recorded for IVF/ICSI stimulation cycles and FET cycles alike. For Denmark, no such direct link exists in the IVF register.

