Date of pregnancy test	Continuous	N/A (used to derive outcome variable)		
Pregnancy test result or indicator for pregnancy	Continuous	N/A (used to derive outcome variable)		
Date of ultrasound	Continuous	N/A (used to derive outcome variable)		
Date of pregnancy loss	Continuous	N/A (used to derive outcome variable)		
Other clinical characteristics				
Height/weight or BMI	Continuous	X	X	
Obesity	Categorical	X	X	
Bariatric surgery	Categorical	X	X	
Smoking status*	Numerical	X	X	

Variable	Measurement scale	Baseline characteristic	Candidate variable for PS	Candidate variable for additional adjustment
Type 1 diabetes mellitus	Categorical	X	X	
Type 2 diabetes mellitus	Categorical	X	X	
Antidiabetic drugs	Categorical	X	X	
History of thromboembolic events	Categorical	X	X	
Use of thrombosis prophylaxis	Categorical	X	X	
Porphyria and other relevant conditions [#]	Categorical	X	X	
History of any cancer	Categorical	X	X	
Medical history, fertility-related				
Number of previous failed COS	Categorical	X	X	
History of failed IUI	Categorical	X	X	
History of COS with a study drug	Categorical	X	X	
History of COS with a non-study drug	Categorical	X	X	
Previous delivery with at least one live birth following IVF	Categorical	X	X	
Parity	Categorical	X	X	
OHSS	Categorical	X	X	
Amenorrhea or oligomenorrhea	Categorical	X	X	
PCOS	Categorical	X	X	
Endometriosis	Categorical	X	X	

Variable	Measurement scale	Baseline characteristic	Candidate variable for PS	Candidate variable for additional adjustment
Female infertility diagnosis	Categorical	X	X	
Female factor infertility*	Categorical	X	X	
Male factor infertility*	Categorical	X	X	
Idiopathic factor infertility*	Categorical	X	X	
Medical history, laboratory test results (value at most recent record on or prior to stimulation cycle index date) [†]				
Anti-Müllerian hormone, pmol/L	Continuous	X	X	
FSH, IU/L	Continuous	X	X	
Thyrotropin, mIU/L	Continuous	X	X	
Prolactin, mIU/L	Continuous	X	X	

BMI: body mass index; COS: controlled ovarian stimulation; FET: frozen embryo transfer; FSH: follicle-stimulating hormone; GnRH: gonadotropin-releasing hormone; ICSI: intracytoplasmic sperm injection; IUI: intrauterine insemination; IVF: in vitro fertilization; IU: international unit; L: liter; mIU: milli-international unit; OHSS: ovarian hyperstimulation syndrome; PCOS: polycystic ovarian syndrome; pmol: picomole; PS: propensity score.

Notes:

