9.7.1 Analysis Sets

To address the study objectives, analysis sets will be constructed based on the study outcomes as defined in Section 9.1.2. To allow for a sufficient time period to assess the outcomes after the initiation of a stimulation cycle, the analysis sets will be restricted to outcome-specific time periods. For the analysis sets, the following outcome-specific time periods are applied: 1 year after the stimulation cycle initiation for LBR, CPR, OPR, MC-CLBR and TTLB; 1 year after the stimulation cycle and linked FET initiation for CLBR, CCPR, COPR, pregnancy loss, multiple pregnancy and treatment-associated costs; 1.5 months after the stimulation cycle initiation for oocyte retrieval and embryos cryopreserved per initiated stimulation cycle, and cycle cancellation; 1 month after the stimulation cycle aspiration for oocyte retrieval and embryos cryopreserved per aspirated stimulation cycle; 4 months after stimulation cycle initiation for OHSS; 3 months after last embryo transfer for implantation. Fresh and frozen embryo transfers will be assessed by using all fresh and frozen embryo transfers done by the end of the study period (31 December 2020).

The analysis sets and their use for the study objectives and outcomes are defined in Table 5. The use of analysis sets will be described in the statistical analysis, and any needed specific modifications or restrictions on the analysis sets needed for the analysis of the study objectives will be further described in the SAP.

Table 5. Description of analysis sets

Analysis set	Description of the analysis set	Study objective(s)	Study outcome measure(s)
Set 1	Stimulation cycles with drug of interest initiated on or before 31 December 2019	Primary objective	LBR
		Secondary objective 1	CPR
			OPR
Set 2	Stimulation cycles with drug of interest and linked FET cycles initiated on or before 31 December 2019	Primary objective	CLBR
		Secondary objective 1	CCPR
			COPR
		Secondary objective 5	Pregnancy loss
		Secondary objective 6	Multiple pregnancy
Secondary objective 9	Treatment-associated costs		
Set 3	Stimulation cycles with drug of interest initiated on or before 15 November 2020 ⁺	Secondary objective 2	Oocytes retrieved per initiated stimulation cycle
			Embryos cryopreserved per initiated stimulation cycle
			Utilizable embryos per initiated stimulation cycle
		Secondary objective 7	Cycle cancellation

Analysis set	Description of the analysis set	Study objective(s)	Study outcome measure(s)

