3	Minimum duration of follow-up for assessment of MC-CLBR and TTLB	The main analyses of the MC-CLBR and TTLB each uses a minimum of 1 year of follow-up and includes women who had initiated their first-ever stimulation	1 year is considered sufficient to achieve at least one live birth and a reasonable number of complete cycles for reliable estimates of the MC-CLBR in view of previous studies considering up to 9 (20) and 8 (21) stimulation cycles for the estimation of cumulative live birth rates with at least 1.5 and 2 years of follow-up, respectively.	Minimum follow-up period extended to 2 years, thus restricting the analysis to women who had initiated their first-ever stimulation cycle on or before 31 December 2018.	The effect of extending the minimum follow-up period on the conservative and optimal estimates of the MC-CLBR and on TTLB will be explored. The analysis of each outcome will otherwise be repeated as described in 9.7.3.3 and 9.7.3.4.

No.	Topic	Main analysis		Sensitivity analysis	
		Method	Justification	Alteration to method	Justification
		cycle on or before 31 December 2019.			
4	CLBR	The main analysis does not consider the possible impact of oocyte yield on CLBR.	Oocyte yield is not considered in the stratified analysis.	CLBR in the first, second and third stimulation cycle will be estimated by the number of oocytes retrieved in the first cycle (cycle rank expressed as observed in the study period).	Oocyte yield is known to be positively associated with CLBR (20,40,41). The effect of oocyte yield in the first cycle will be explored for the CLBR. Otherwise the analysis will be repeated as described in 9.7.3.3 and 9.7.3.4, although rates will only be reported for the IPTW-weighted cohorts.

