9.9.4 Unmeasured Confounding

Although a broad range of characteristics will be collected for this study, some relevant predictors of treatment outcomes, such as the antral follicle count and anti-Müllerian hormone levels (60,61),

will not be available from the data collected in Sweden and likely only available for a subset of the Danish study population. Unmeasured confounding cannot be ruled out. However, a sensitivity analysis performed for Denmark will explore the effect of controlling for anti-Müllerian hormone levels and other relevant outcome predictors available from the RLRR (see Analysis 4 in Table 8).

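### Per-cycle outcomes pool first and repeat stimulation cycles, but the propensity score candidates omit oocyte yield and cancellation in the previous cycle, which both IVF registers record

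*Protocol*

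**What the plan says.** **Pooling.** Section 9.7.1, Table 5, defines the LBR set as "Stimulation cycles with drug of interest initiated on or before 31 December 2019", with no restriction to first cycles. The CLBR set is built in the same way with linked FET cycles added. Section 9.2.2 says "A woman may contribute maximum five stimulation cycles to the same cohort if she had several cycles with the same study drug", and also "She may contribute cycles to more than one study cohort if she had distinct stimulation cycles with different study drugs". The planned strata in Section 9.7.3.6 are age and GnRH protocol, not cycle rank.

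**Control of treatment history.** Section 9.2.2 states: "History of IVF/ICSI treatment, including with a non-study gonadotropin, will be controlled for in the analysis (in the PS estimation". Section 9.7.3.1 ties the PS to the covariates marked in Table 1 (Section 9.3.2). The candidates there that describe earlier treatment are "Number of previous failed COS", failed IUI, COS with a study drug, COS with a non-study drug, previous IVF live birth, parity and OHSS. Oocyte number in an earlier cycle is not listed. Cycle cancellation appears only as a variable for deriving an outcome.

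**Availability and relevance.** Section 9.1.2.2 ascertains both oocytes retrieved and cycle cancellation in the IVF registers. Table 8, Analysis 4, says: "Oocyte yield is known to be positively associated with CLBR". Section 9.9.4 says of antral follicle count and anti-Müllerian hormone (AMH) that they "will not be available from the data collected in Sweden and likely only available for a subset of the Danish study population".

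**The concern.** From the second cycle on, the clinician knows how the woman responded last time. Take two women with one failed COS each, one with 2 oocytes retrieved and the other with 15. On the listed treatment-history items they look alike, unless the high responder had OHSS. If women with a poor previous response go more often to one product, that product's live birth rate per cycle falls whatever its effect, and weighting on the listed history cannot fully correct this.

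The previous yield matters more because direct measures of ovarian reserve are largely missing. For repeat cycles it is a recorded, response-based substitute in both countries. It also meets the protocol's own rule in Section 9.3.2, which keeps out of the PS only variables determined after the gonadotropin has been chosen.

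At stake are two of the three primary measures (LBR and CLBR) and the per-cycle and per-pregnancy secondary outcomes.

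**Working it through.** **1. The plan's own counts.** Section 9.5 multiplies total cycles by the share of each drug. Danish reference product from 2010: 100,000 × 0.53 = 53,000, as in Table 2. Six of the eight cycle counts reproduce within 3%. The other two are Danish biosimilars (58,000 × 0.10 = 5,800 against 5,000) and Swedish reference product from 2014 (65,000 × 0.35 = 22,750 against 22,000). Both rest on rounded percentages and do not affect the point.

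**2. Share of repeat cycles on the same product** = 1 − women/cycles, from Table 2:

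| Cohort | Women / cycles | Repeat share |
|---|---|---|
| Denmark, reference, from 2010 | 19,000 / 53,000 | 64% |
| Denmark, HP-hMG, from 2010 | 12,000 / 33,000 | 64% |
| Denmark, reference, from 2014 | 14,000 / 31,000 | 55% |
| Denmark, biosimilars, from 2014 | 3,000 / 5,000 | 40% |
| Sweden, reference, from 2010 | 18,000 / 42,000 | 57% |
| Sweden, HP-hMG, from 2010 | 17,000 / 40,000 | 58% |
| Sweden, reference, from 2014 | 11,000 / 22,000 | 50% |
| Sweden, biosimilars, from 2014 | 10,000 / 18,000 | 44% |

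These shares are approximate. Section 9.5 models the number of women by assuming that those without a delivery continue the same drug the next year. Ignoring dropout and switching in this way lowers the count of women and raises the repeat share. In the other direction, a first cycle on one product may follow a cycle on another, and the formula does not count it as a repeat.

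**3. Illustrative bias in LBR.** Assumed, not in the protocol: LBR 12% after a poor previous response and 25% otherwise; repeat share s of 0.4 or 0.6; poor-responder share q among repeat cycles still unequal between cohorts after weighting.

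LBR = s[0.12q + 0.25(1 − q)] + 0.25(1 − s), so the spurious difference is s × Δq × 0.13.

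| q in the two cohorts | s | LBR in the two cohorts | Difference | OR |
|---|---|---|---|---|
| 15% vs 25% | 0.4 | 24.22% vs 23.70% | 0.52 points | 1.03 |
| 15% vs 25% | 0.6 | 23.83% vs 23.05% | 0.78 points | 1.04 |
| 10% vs 25% | 0.4 | 24.48% vs 23.70% | 0.78 points | 1.04 |
| 10% vs 25% | 0.6 | 24.22% vs 23.05% | 1.17 points | 1.07 |

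A wider grid of assumptions (Δq 2 to 15 points, live birth risk difference 5 to 15 points, s 0.40 to 0.64) runs from 0.40 × 0.02 × 0.05 = 0.04 points to 0.64 × 0.15 × 0.15 = 1.44 points.

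**4. Yardstick.** Section 9.5 claims detectable differences of 1.5 points against HP-hMG, and of 2.5 points (Denmark) and 2.0 points (Sweden) against biosimilars. These were calculated per woman for MC-CLBR at 50% and then stated for the primary outcomes generally.

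**5. Do the sensitivity analyses in Table 8 cover it?**
- Analysis 4 concerns CLBR only. It groups cycles by yield in the first cycle, not the preceding one, and does not put yield in the PS. For the first cycle it conditions on a result of the product under study.
- Analysis 6 adjusts LBR, CLBR and MC-CLBR for laboratory results, but only in the Danish subset that has them. (The Table 1 footnote and Section 9.9.4 call it Analysis 4.)

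**The case against.** **Response-guided choice is not documented.** A reader might infer that the protocol shows previous response steering the next product. It does not. Section 9.9.3 says the drugs are equally recommended and used interchangeably. Without that link there is no confounding by this route. This stands, so the mechanism must be stated as an assumption. The same section concedes, however, that the cohorts may differ in previous IVF treatment.

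**Other candidates carry part of the information.** Age, BMI, PCOS, female infertility diagnosis and OHSS are in the PS. OHSS covers excessive response, and a cancelled cycle may count as a failed one. This reduces the residual imbalance, but no listed item measures a poor response in the previous cycle.

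**First-cycle results exist.** A reader might infer that results free of earlier treatment are never shown. That is too strong. Section 9.7.3.3 restricts MC-CLBR to women starting their first-ever cycle and reports it by rank, so rank 1 is a first-cycle cumulative result. TTLB has the same restriction. The gap concerns LBR and the other per-cycle and per-pregnancy outcomes.

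**Wording of objectives 5 to 8.** Section 8.2 has, for example, "Rate of pregnancy loss for the first (and successive) IVF/ICSI stimulation cycle(s". This could be read as a promise of separate first-cycle results, but also as covering all cycles, which pooled rates satisfy. It supports the request for first-cycle results without proving a contradiction.

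**Drug history by product.** Table 1 makes history of COS with a study drug categorical and does not say that products are merged. Splitting it is a matter for the SAP.

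**Previous yield is not a pure measure of reserve.** Section 7 cites trials with more oocytes on the reference product than on hMG, such as means of 11.8 and 10.0. This stands as a caution about the fix.

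**Conclusion.** The omission is real and cheap to repair. Two covariates that precede treatment and are recorded in both registers are missing from a PS list that is meant to control for IVF history, in analyses where about 40% to 64% of cycles are repeats on the same product. That range is approximate and should not be read as a minimum.

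Whether the odds ratios are actually biased depends on response influencing product choice, which the protocol neither states nor excludes. Under the main assumed inputs the bias is 0.5 to 1.2 points (OR 1.03 to 1.07). Every such scenario lies below the smallest claimed detectable difference of 1.5 points, so the figures do not show that confounding alone would produce a significant result. They show that it could be a sizeable part of an effect of the size sought. With smaller imbalances it is negligible. MC-CLBR and TTLB are outside the point.

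**What to change.** 1. Add two PS candidates to Table 1: oocytes retrieved in the most recent previous stimulation cycle, in categories that include one for no previous cycle; and cancellation of that cycle before aspiration. Where an earlier cycle has no recorded yield, the missing-data category of Section 9.7.2 applies.
2. Keep the earlier product in the PS, because previous yield partly reflects it.
3. Add to Table 8 a sensitivity analysis of LBR and of objectives 5 to 8 restricted to first-ever stimulation cycles. For cumulative live birth, refer to MC-CLBR at rank 1.

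**Cost:** wording in Table 1, Table 8 and the SAP, and one further subset run. Both variables are already to be obtained as outcomes. Intervals will be wider in the first-cycle subset.

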The Danish Medical Birth Register (DMBR) is an enrichment of data already recorded in the DNPR and compiles relevant information of pregnancies that has led to childbirth in Denmark at home or in a hospital (30). It contains information on characteristics of mother and child, pregnancy and delivery characteristics including induction procedures and gestational age, outcomes of pregnancy and delivery, and the mother's history of previous abortions and/or deliveries. The DMBR includes linkage between infant, mother and father. The DMBR has been in operation since 1973, with later improvements, particularly in 1997. The register is updated once a year after end of December with a lag of 13 months, partly due to the enrichment on information on date of death within the first year after birth.

The Danish Register of Medicinal Product Statistics (RMPS) contains patient-level data on all prescription drugs filled by patients at community pharmacies (31,32), but not medication administered at hospitals. The administrative purpose of the register is to administer how the cost is split between the health care system, the municipality and the patient's co-payment. Thus, completeness and accuracy of data collection is very high. The register contains information on the date of purchase, item number, product name, ATC code, strength per unit, quantity of DDDs (as per the World Health Organization (WHO)) per package and number of packages filled. Data is available from 1995 and onwards. Since April 2004, information on medical indication for prescription and daily prescribed dose by physician has also been available, but completeness and validity are affected by a non-compulsory obligation to record this information.

The Danish Register of Laboratory Results for Research (RLRR) is managed by the Danish Health Data Authority. It has information on laboratory tests at the country's major clinical biochemical and clinical immunological laboratories. Laboratory results are first collected in the National Lab Databank. General practitioners, specialists in private practices and private fertility clinics can forward samples for analysis to the hospital laboratories, when they do not have the capacity/equipment to do the analysis themselves, and these tests are also included in the National Lab Databank. All this information is transferred to the RLRR later. If a patient, proactively, has denied consent to exchange lab results, the results are not transferred to the RLRR.

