9.7.3.1 Propensity Score Methodology

PS-based methods are frequently used in non-interventional studies to control for confounding when estimating treatment effects (38). In this study, the PS weighting will be implemented using IPTW approach.

PS, typically obtained using logistic regression models, are covariate summary scores that indicate the individual probability of having a treatment initiated with the study drug against the comparator drug, given the observed baseline characteristics. In PS weighting with IPTWs, each subject is weighted by the inverse probability of receiving the treatment they have actually received, *i.e.*, $1/PS$ in the study drug cohort and $1/(1-PS)$ in the comparator drug cohort (22). In other words, the PS weighting with IPTW creates a pseudo-population of study drug cohort and the comparator drug cohort that are weighted samples of the original study cohorts but have the same covariate distribution as the overall original study cohorts (22). Thus, using the IPTW-weighted study cohorts will remove confounding from all covariates included in the PS model, and give the estimate for the treatment effect in the overall population (22).

For this study, the IPTW approach will be based on pairwise PS estimation for i) rhFSH-alfa reference product cohort and HP-hMG cohort, and ii) rhFSH-alfa reference product cohort and rhFSH-alfa biosimilars cohort. The PS will be estimated for the stimulation cycle initiation with the study drug (rhFSH-alfa reference product) against the comparator drug (HP-hMG or rhFSH-alfa biosimilar product) by using logistic regression, including covariates as indicated in Table 1 (Section 9.3.2). Based on the estimated pairwise PS, i) IPTW-weighted rhFSH-alfa reference product cohort and IPTW-weighted HP-hMG cohort, as well as ii) IPTW-weighted rhFSH-alfa reference product cohort and IPTW-weighted rhFSH-alfa biosimilars cohort will be created.

Diagnostic measures will be used for assessing the success of the PS model to account for confounding. In addition, the distribution of IPTWs will be checked and in case very large weights are observed, the stabilized, trimmed and truncated weights will be considered to avoid increasing the variability of the treatment effect estimates due to very large weights (38).

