Prior to October 2016, induced abortions were not recorded in the SNPR, meaning ascertainment of this component of pregnancy loss will rely solely on the Q-IVF prior to this date. Furthermore, abortion statistics based on anonymized data show that ~70% of all induced abortions between 2018 and the second quarter of 2020 were medical abortions completed at home (59). This suggests the data on induced abortions captured in the SNPR in 2016-2020 is likely incomplete.

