14.3 Additional Information

All code lists included below may be subject to amendment or revision during study conduct.

14.3.1 Outcome variables (Section 9.1.2): Diagnosis and Procedure Codes for Definition and Databases for Identification

Outcome	Code for identification ⁺	Comment	Source for identification
Primary outcome			
Live birth	N/A		DMBR, SMBR, Q-IVF
Secondary outcomes			
Clinical pregnancy	ICD-10: O00 NOMESCO procedure codes: MCB 00, LAA 20, LBC*	Intrauterine pregnancy ascertained in the DIVF and Q-IVF. ICD-10: Ectopic pregnancy NOMESCO procedures: laparotomy and delivery of extrauterine fetus, percutaneous or transvaginal injection into ovarian pregnancy, tube conserving operations for tubal pregnancy	DIVF, Q-IVF, DNPR, SNPR
Ongoing pregnancy	ICD-10: O03, O04, O05, O06 [#] NOMESCO procedure codes: LCH*	Delivery and gestational age at delivery ascertained in the DMBR and SMBR. For Sweden, miscarriage and induced abortion† will be ascertained in the SNPR and Q-IVF. ICD-10: spontaneous abortion, medical abortion, other abortion, unspecified abortion NOMESCO procedures: procedures related to termination of pregnancy	DMBR, SMBR, DNPR, SNPR, Q-IVF
Oocytes retrieved	N/A	Ascertained using information recorded in the DIVF and Q-IVF.	DIVF, QIVF
Embryos transferred			
Embryos cryopreserved			
Implantation			
Pregnancy loss	ICD-10: O03, O04, O05, O06 [#] NOMESCO procedure codes: LCH*	ICD-10: spontaneous abortion, medical abortion, other abortion, unspecified abortion NOMESCO procedures: procedures related to termination of pregnancy	DNPR, SNPR, Q-IVF

Outcome	Code for identification ⁺	Comment	Source for identification
		For Sweden, miscarriage and induced abortion† will be ascertained in the SNPR and Q-IVF.	

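### Previous spontaneous loss, ectopic pregnancy and earlier IVF/ICSI clinical pregnancy are not propensity score candidates, so residual confounding of the pregnancy-loss comparison, and less so of later-cycle LBR and CLBR, is possible and unacknowledged

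*Protocol*

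**What the plan says.** Section 9.7.3.1 estimates the propensity score by logistic regression, "including covariates as indicated in Table 1", and says that the weighted cohorts "will remove confounding from all covariates included in the PS model". The protocol itself therefore fixes which histories can be balanced.

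The fertility-related block of Table 1 (Section 9.3.2) contains:
- number of previous failed stimulations and history of failed IUI;
- history of stimulation with a study or a non-study drug;
- "Previous delivery with at least one live birth following IVF", and parity;
- OHSS, menstrual disorder, PCOS and endometriosis;
- infertility diagnosis and infertility factors.

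Pregnancy loss appears in Table 1 only as a date used to derive an outcome. Section 14.3.3, which holds the covariate codes, has none for miscarriage or ectopic pregnancy. Those codes appear only in Section 14.3.1, for outcomes: O00 for ectopic pregnancy, and O03–O06, glossed as "ICD-10: spontaneous abortion, medical abortion, other abortion, unspecified abortion".

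Pregnancy loss is secondary objective 5 (Section 8.2). Section 9.9.4 names antral follicle count and anti-Müllerian hormone as predictors that may be missing. It does not mention earlier loss or ectopic pregnancy.

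**The concern.** A woman's earlier losses may predict loss in her next pregnancy, and having conceived before may predict live birth. Either could also influence which product is used next. Women may change product between cycles and contribute to more than one cohort (Sections 9.1.1 and 9.2.2), and the result of the previous cycle is known when the next product is chosen. If these histories differ between cohorts after weighting, two equal products could show a difference in a safety outcome, and a smaller one in per-cycle live birth.

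The protocol treats a comparable case differently. OHSS is a safety outcome and its history is a candidate; pregnancy loss is a safety outcome and its history is not.

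**Working it through.** **Do the listed covariates already carry the information?** Section 9.7.3.3 and Table 8 (analysis 2) treat an attempt as failed when no live birth followed. On that meaning, the count of failed stimulations puts a cycle that ended in a lost clinical pregnancy in the same class as one with no conception. Parity and previous IVF live birth record deliveries, not losses. Drug history says what was used, not whether conception followed. These are partial proxies; none separates loss from non-conception.

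**Can the history be measured?** In part.
- Patient registers: ICD-10 diagnoses can be used from 1994 (Denmark) and 1998 (Sweden) (Section 9.2.3). Neither register covers primary care (Sections 9.4.1 and 9.4.2).
- Danish IVF register: ultrasound gestational-sac results from 2006, so earlier IVF clinical pregnancy is visible. Pregnancy outcome is not recorded.
- Q-IVF: pregnancy outcome, from 2007.
- Danish birth register: holds the mother's "history of previous abortions and/or deliveries", but only for pregnancies that ended in childbirth.
- Swedish birth register: no spontaneous losses.
- Induced abortion: "Prior to October 2016, induced abortions were not recorded in the SNPR" (Section 9.9.2). A history limited to spontaneous loss avoids this gap.

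**Which analyses are exposed?** Sets 1 and 2 (Table 5) pool all eligible cycle ranks, so LBR, CLBR and pregnancy loss include later cycles. Set 8 (MC-CLBR, TTLB) starts at the first-ever stimulation cycle, when no earlier IVF conception exists.

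**How large could it be?** The plan gives no figure to reproduce. What follows is illustration. The risks and prevalences are assumptions, and the imbalances are those left after weighting.

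*Pregnancy loss.* Loss rate = 0.20 × [1 + (RR − 1) × prevalence of previous loss], with equal products.

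| Prevalence | RR | Loss rates | OR |
|---|---|---|---|
| 20% vs 20% | any | equal | 1.00 |
| 20% vs 25% | 1.3 | 21.2% vs 21.5% | 1.02 |
| 20% vs 25% | 2.0 | 24% vs 25% | 1.06 |
| 20% vs 30% | 1.3 | 21.2% vs 21.8% | 1.04 |
| 20% vs 30% | 2.0 | 24% vs 26% | 1.11 |

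For example, the last row is (0.26/0.74)/(0.24/0.76) = 1.11.

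*LBR in later cycles.* Assume 20% without an earlier conception and 25–28% with one. Spurious difference = prevalence difference × LBR difference.
- Low case: (25% − 20%) × 5 points = 0.25 point. Rates 21.25% vs 21.0%, OR 1.02.
- High case: (25% − 15%) × 8 points = 0.8 point. Rates 22.0% vs 21.2%, OR 1.05.

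*Dilution by first cycles.* Cycles and women in Table 2 give a crude share of cycles beyond the first with a drug: from 1 − 3,000/5,000 = 40% (Danish biosimilars) to 1 − 19,000/53,000 = 64% (Danish reference product from 2010). If the share is the same in both cohorts, the pooled LBR effect is 0.40 × 0.25 = 0.10 to 0.64 × 0.8 = 0.51 point. For scale only, Section 9.5 states detectable differences of 1.5–2.5 points, calculated for MC-CLBR.

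**The case against.** The strongest reply is that confounding needs a link between these histories and product choice after weighting on age, clinic type, parity, failed stimulations, drug history, previous IVF live birth and infertility diagnosis. No section states such a link, and Section 9.9.3 says the products are used interchangeably. That a product is kept after a conception and changed after none is conjecture. The imbalances above are assumed too. This stands: a reader might infer that the comparisons *are* confounded by earlier loss, and the documents do not show it.

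A reader might also infer that every live birth measure is affected in this way. The mechanism through earlier IVF conception cannot operate for MC-CLBR or TTLB. For LBR and CLBR even the direction is unclear: previous loss may lower live birth, while a woman with a loss has also conceived, which may raise it.

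Thirdly, a reader might infer that the registers hold this history in full. They do not, as the register list shows.

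It can also be said that Table 1 is broad, that code lists may be revised (Section 14.3) and that Section 9.9.4 already concedes unmeasured confounding. This carries less weight. Section 9.9.3 says baseline differences cannot be ruled out and promises adjustment for factors potentially associated with the outcomes. The concession in Section 9.9.4 gives as examples predictors that are unavailable or incomplete, whereas these histories are largely obtainable from sources the study already accepts for its outcomes. Incomplete capture limits the benefit of adding them; it does not justify omitting them.

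**Conclusion.** The omission is real and lies in the protocol's own covariate list. It leaves possible, not demonstrated, residual confounding, chiefly of secondary objective 5 and to a lesser extent of LBR and CLBR in later cycles. The size is unknown from the documents and is zero if prevalence is equal after weighting. Under the assumed inputs it is modest: a loss OR up to about 1.11, and less than 1 point of LBR in later cycles before dilution. This is a worthwhile, inexpensive improvement in confounding control and a gap in the stated limitations, not a flaw that invalidates the primary comparison.

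**What to change.** Add to Table 1 and Section 14.3.3, as propensity score candidates measured before the stimulation cycle index date:
- previous spontaneous loss (0, 1, 2 or more): O03 in the Danish and Swedish patient registers, plus pregnancy outcome in Q-IVF;
- previous ectopic pregnancy (yes/no): O00 in both patient registers;
- any earlier clinical pregnancy after IVF/ICSI (yes/no): gestational-sac data in the Danish IVF register, and Q-IVF. Use it for the per-cycle analyses only, not for MC-CLBR or TTLB.

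Report the balance of all three before and after weighting. In Section 9.9.4, name the residual gap: losses managed in primary care or at home are missed, the Swedish birth register holds no losses, the Danish birth register history covers only women with a birth, and Q-IVF starts in 2007.

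The cost is three more covariates and a few lines of text. No new data source is needed. Control will be partial, and completeness will differ between the two countries.
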